### 7.23 Reconstitution

Reconstitute each vial with NS, sterile water, or D5W to achieve a final concentration of 10 mg/ml.

Further dilution to concentrations as low as 0.5 mg/ml with NS or D5W is acceptable.

### 7.24 Stability

Discard infusion solution 8 hours after preparation, since it contains no antibacterial preservative.

### 7.25 Toxicities

Myelosuppression, nausea and vomiting, transient liver function abnormalities, paresthesia and high frequency hearing loss, abnormalities in serum creatinine and creatinine clearance, proteinuria, hypocalcemia, and hypomagnesemia.

## **8.0 RESPONSE CRITERIA**

The same method used to quantitate tumor status prior to starting this study must be used to measure tumor status after treatment. Therefore, only MRI scans will be used to determine response or progression of disease.

- Complete Response (CR): Complete resolution of tumor on MRI scan
- Partial Response (PR): A reduction of at least 50% in tumor area of bidimensional measurable lesions. In addition, there can be no appearance of new lesions or progression of any lesion.
- Stable Disease (SD): A decrease of less than 50% or an increase of less than 25% in the tumor area of bidimensional measurable lesions .
- Progressive Disease: Greater than a 25% increase in the bidimensional tumor area compared to the immediate pre-study area or compared to area of best prior response at that site, or the reappearance of tumor in sites of involvement which had responded completely to therapy (including surgery), or appearance of tumor in a previously uninvolved area.

## **9.0 CRITERIA FOR REMOVAL FROM PROTOCOL THERAPY, FOLLOW-UP, AND OFF STUDY CRITERIA**

### **9.1 Criteria for Removal from Protocol Therapy**

Patients may be removed from protocol therapy prior to completion under the following circumstances:

- a) Disease relapse/progression (see Section 8.0)
- b) Parent/patient request
- c) Death
- d) Physician or investigator's discretion

Discontinuation for other reasons will be considered protocol deviations.

### **9.2 Removal from Protocol Follow-up**

Patients may be removed from protocol specified follow-up under the following circumstances:

- a) Death
- b) Parent/patient request
- c) Entry onto a sanctioned second line therapeutic study or follow-up study.

## **10.0 NEURORADIOLOGY GUIDELINES**

### **10.1 Whole Brain MRI With and Without Contrast**

To document the degree of residual tumor, postoperative MRI scan, with and without contrast, must be done prior to beginning therapy. For patients who undergo stereotactic biopsy only, a post-operative MRI is not required. For patients with M2 and M3 disease, a post-op MRI is strongly encouraged, but not mandatory.

Postoperative MRI should be done within 72 hours of surgery, when there is less edema or postoperative enhancement, which can make measurements of residual tumor difficult. An MRI with

and without contrast should be done 4 weeks after the completion of radiotherapy, prior to cycle 4 and one month after cycle 6 of maintenance chemotherapy, during follow-up, and at relapse .

## **10.2 Pre- or Post-operative Spinal Axis Imaging**

An MRI with and without gadolinium of the entire spine (through the inferior extent of the thecal sac) is required either 7 days prior to or within 28 days after surgery and at relapse. If an MRI scan is performed within 7 days prior to surgery, then only a post-contrast examination is necessary.

**Note: a pre-operative MRI scan of the spine is preferable for patients with posterior fossa tumors because surgically-induced inflammation/blood can be difficult to distinguish from tumor.**

## **11.0 NEUROSURGICAL GUIDELINES**

### **11.1 Types of Surgery**

A craniotomy or craniectomy is necessary to remove the bulk of the tumor, to reestablish CSF circulation, and to provide tissue for diagnosis. The goal of the operation should be a gross total resection unless involvement of vital structures or widely disseminated disease makes this impractical. In the posterior fossa, a gross total resection should be accomplished unless there is invasion of the floor of the fourth ventricle, middle cerebellar peduncle, cerebellar pontine angle, or other brain stem structures. In the supratentorial space, a gross total resection should be accomplished unless the tumor invades deep structures, such as the hypothalamus, or functionally important cortex, such as the motor or speech cortex. If the tumor appears near functionally important cortex on the pre-operative scan, consideration should be given to intraoperative cortical mapping with the aim of sparing functional cortex while achieving the greatest tumor resection possible.

If the post-operative MRI scan (obtained within 72 hours of the operation) reveals residual resectable tumor, a second operation should be considered to remove the remaining tumor. Few, if any, patients should be entered into this study with biopsy only or partial resections.

Biopsy alone, with no attempt at resection, may be associated with a statistically worse survival and should not be done except in the setting of widely metastatic disease and a small primary tumor.

No patient will be entered without a diagnosis established by microscopic examination of tumor tissue.

## **11.2 Staging Criteria**

### **11.21 Extent of Resection/Surgical Confirmation**

a) Biopsy Only: If tumor removal is less than 10% of the total tumor mass, this will be considered a biopsy only.

b) Partial Resection: The surgical removal of greater than 10%, but less than 50%, of the tumor mass.

c) Sub-total Resection: The surgical removal of greater than 50%, but less than 95%, of the tumor mass.

d) Radical Subtotal Resection (Near Total): The surgical removal of greater than 95%, but less than 100% of the tumor mass.

e) "Gross Total" Resection: No visible tumor is left at the time of surgery and is confirmed by postoperative CT or MRI.

### **11.22 Metastasis Stage (M0-M4)**

The surgeon should inspect the regional leptomeninges and a decision should be made as to whether metastatic nodules are present in the arachnoid or whether the entire leptomeningeal surface is infiltrated with tumor. If there is any question, a small segment of arachnoid should be excised and sent as a separate specimen.

### **11.23 MRI Confirmation**

All patients will have confirmation of the neurosurgical assessment of the extent of resection with a postoperative MRI scan, without and with contrast. This scan should be carried out within 72 hours postoperatively. Bidimensional measurements of residual tumor volume should be obtained. For

patients who undergo stereotactic biopsy only, a post-operative MRI is not required. For patients with M2 and M3 disease, a post-op MRI is strongly encouraged, but not mandatory.

### **11.3 Peri-operative Corticosteroids**

Some patients with large tumors may require corticosteroid therapy preoperatively to reduce associated cerebral edema.

- a) Usual corticosteroid dosage is 0.25 to 1 mg/kg/day of dexamethasone, in divided doses, every 4-6 hours.
- b) Corticosteroids may be continued during the peri-operative period, but the dosage, dose interval and duration of steroid therapy must be noted, and every attempt made to taper and discontinue corticosteroid therapy as soon as clinically feasible.

### **11.4 Pathology Studies**

As much tumor as possible should be sent for pathology and biologic studies. Tissue should go directly to the institutional pathologist in saline (wrapped towel) prior to fixation in formalin for histologic diagnosis.

### **11.5 Shunts**

- a) Children may need preoperative external ventricular drains, if they are symptomatic because of tumor-induced hydrocephalus.
- b) After removal of the tumor and the external drains, approximately 30% of patients with medulloblastoma/PNET will require a CSF shunt because of permanent hydrocephalus.
- c) The routine use of pre-operative shunts or shunt filters is not encouraged.

## **12.0 RADIATION THERAPY GUIDELINES**

The craniospinal and boost radiation techniques outlined below are standard for this tumor.

ATTENTION: The radiotherapy guidelines for this protocol do not allow for treatment breaks except in the setting of clinical instability.

## **12.1 Timing of Radiation Therapy**

All patients shall receive irradiation to the cranio-spinal axis (CSA) followed by a boost to the primary tumor site (posterior fossa or supratentorial) as well as to CNS metastatic sites. All patients shall begin radiation treatments after registration on study and within 35 days of definitive surgery.

## **12.2 Equipment**

### **12.21 Modality**

Photon irradiation shall be used.

### **12.22 Energy**

The cranial field should be treated with megavoltage photons with energies in the range of 4 – 6 MV.

The primary site boost will usually be given with similar energy, but for centrally located primary tumors, the boost may be given with a photon beam of higher energy. In such cases, an isodose plan should be submitted with the quality assurance material. Photon of energy 4 to 6 MV will generally be used for spinal irradiation but electrons of suitable energy may be used.

### **12.23 Geometry**

All patients must be treated on isocentric machines. All machines must have a minimum source-to-axis distance (SAD) of 80 cm. Treatments may be given with fixed SSD techniques.

### **12.24 Simulator**

All patients must be simulated on a dedicated radiation therapy simulator.

### **12.25 Immobilization Devices**

For craniospinal irradiation, immobilization devices such as head holders or custom mold are required.

Head immobilization with a thermoplastic mask or head frame is required when 3D treatment planning is used. The immobilization device should limit daily motion to a maximum of  $\pm 3-5$ mm.

## 12.3 Treatment Volume Anatomical Description

### 12.31 Treatment Volumes

Definitions:

- Gross Target Volumes (GTV): The Gross Target Volume (GTV) is based upon the T1 weighted MRI with and without Gadolinium contrast. Identification of the GTV shall be based upon pre-operative extent and anatomic shifts or changes after surgery. The GTV should include any residual enhancing tumor mass and the wall of the resection cavity.
- Clinical Target Volume (CTV): The Clinical Target Volume (CTV) is defined as the GTV plus a 1.5-cm margin
- Planning Target Volumes (PTV): The Planning Target Volume (PTV) margin should be an additional 0.3 to 0.5 cm around the CTV, depending on the setup error of the treatment modality used. In treatment planning, shielding of critical structures should be attempted. At least 95% of the prescribed study dose (55.8 Gy) must encompass at least 95% of the PTV as shown by DVH. No part of the PTV should receive less than 50 Gy.
- Treated Volume (TV): The volume enclosed by an isodose surface that is selected and specified by the radiation oncologist to which the prescribed dose is delivered.

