### 12.32 Treatment Volume

The target volume for the initial portion of the treatment is the entire cranio-spinal axis (the entire subarachnoid space). The target volume for the boost is the tumor bed and the residual tumor if the primary site is in the infratentorial region of the brain. The target volume for the boost for supratentorial tumors is 1 cm around the tumor as seen on the pre-surgical MRI scan. Metastatic tumors will receive boost irradiation with a 1 cm margin around the tumor as seen on a pretreatment MRI scan. 3D treatment planning may be used to plan the boost portion of the treatment.

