### 12.35 Supratentorial Boost

The treatment volume for a supratentorial boost will be defined using a 1 cm margin around the presurgical MRI defined tumor volume. In the event of proximity to normal tissue structures, this margin may be reduced to 0.5 cm to allow for shielding of critical structures. If the margins are reduced to 0.5 cm, this should be clearly stated and justified in the submitted QA documentation. As the total dose to the optic chiasm and both optic nerves should not exceed 50.4 Gy, these structures should be blocked accordingly. A supratentorial boost set up to treat metastatic disease (M2) should meet the same guidelines as that for a boost for a primary supratentorial tumor.

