#### 12.44 Dose Prescription

The radiation dose will be calculated and normalized to the isocenter of the beams used for treatment. The 95% isodose surface will be required to completely encompass the PTV.

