#### 12.532 Primary Site Boost

All patients with primary tumor in the posterior fossa will receive a boost of 32.4 Gy to the posterior fossa. All patients with a supratentorial primary tumor will receive a boost 32.4 Gy to the volume described in section 12.3. As noted there, the total dose to the optic chiasm and both optic nerves should be limited to 50.4 Gy. In addition, if the boost volume occupies more than 2/3 of the supratentorial compartment, the boost dose should be limited to 27 Gy.

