#### 12.533 Metastatic Site Boost

Patients with M1 disease will receive no additional boost. Patients with M2 disease (intracranial subarachnoid disease) will receive boosts of 32.4 Gy to focal areas of supratentorial or posterior fossa metastatic disease. If the volume of a boost to the supratentorial compartment exceeds 2/3 of the

supratentorial compartment volume, the boost will be limited to 27 Gy. The boost dose to the optic chiasm and both optic nerves must be limited to 27 Gy. 3D treatment planning may be used for boosting M2 disease. If 3D planning is used, definitions boost volumes for M2 disease will be the same as specified for boosts to the primary tumor. Patients with M3 disease (spinal deposits of disease) are subdivided into those with diffuse disease and those with focal disease. Diffuse spinal disease is defined as radiographically visible multiple sites of disease in each of at least 3 out of 4 spinal regions (i.e., cervical, thoracic, lumbar or sacral).

If there is diffuse involvement of the spine, the entire spine will be treated to 23.4 Gy. An MRI scan of the spine should be performed when the spine has received 23.4 Gy, and areas of visible disease remaining at that point should be boosted to 45 Gy when above the termination of the spinal cord and 50.4 Gy when below the termination of the cord. If there are focal areas of spinal deposits which do not meet the definition of diffuse involvement defined above, the entire spine will be treated to 23.4 Gy. The focal areas of tumor seen on the initial spinal MRI will be boosted to 45 Gy. Focal deposits below the termination of the cord as defined by the initial MRI will be boosted to 50.4 Gy. The margin for boosting metastatic deposits will be at least 7 mm, and preferably 10 mm.

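### Section 12.31 fixes PTV coverage at 95% of 55.8 Gy for all boosts, although the protocol prescribes 45 or 50.4 Gy in total for some of them

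*Protocol*

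**What the plan says.** Protocol section 12.31 sets out GTV, CTV, PTV and treated volume as definitions and names no tumor site. Under PTV it gives two absolute dose criteria: "At least 95% of the prescribed study dose (55.8 Gy) must encompass at least 95% of the PTV as shown by DVH" and "No part of the PTV should receive less than 50 Gy". Section 12.34 repeats both for the posterior fossa boost.

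The prescriptions are in section 12.53:

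- The craniospinal dose is 23.4 Gy (12.531) and the standard primary boost is 32.4 Gy (12.532).
- For supratentorial primaries, "if the boost volume occupies more than 2/3 of the supratentorial compartment, the boost dose should be limited to 27 Gy". Section 12.533 sets the same cap for supratentorial metastatic boosts: "supratentorial compartment volume, the boost will be limited to 27 Gy".
- Spinal deposits are boosted to 45 Gy above the end of the cord and to 50.4 Gy below it (12.533).
- Section 12.532 also states that "the total dose to the optic chiasm and both optic nerves should be limited to 50.4 Gy".

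Supratentorial boosts have their own volume. In 12.32: "The target volume for the boost for supratentorial tumors is 1 cm around the tumor as seen on the pre-surgical MRI scan". In 12.35: "The treatment volume for a supratentorial boost will be defined using a 1 cm margin around the presurgical MRI defined tumor volume". Neither section gives a PTV or a coverage dose. Section 12.44 has a relative rule, normalized to the isocenter: "The 95% isodose surface will be required to completely encompass the PTV".

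**The concern.** A coverage rule should follow the prescription. Section 12.31 instead carries a fixed number that matches only the 55.8 Gy prescription. No sentence exempts or rescales it for boosts prescribed to less, and none says which rule gives way. Coverage in 12.31 is phrased as an obligation, so its wording does not rank it below the 27 Gy cap.

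At stake is the dose to a large brain volume, or to the spine, in a trial whose purpose is to limit radiation injury. A planner who took 12.31 at face value would exceed a limit set elsewhere in the same protocol. A planner who kept to the limit would depart from the written coverage figure.

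**Working it through.** **Inputs.** Craniospinal dose 23.4 Gy (12.531). Standard boost 32.4 Gy and capped boost 27 Gy (12.532, 12.533). Spinal totals 45 and 50.4 Gy (12.533). Daily dose 1.8 Gy (12.541). Coverage at 95% of 55.8 Gy with a 50 Gy floor (12.31). Central-plane homogeneity of +5% (12.551).

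**The protocol's own figure.** 23.4 + 32.4 = 55.8 Gy, and 55.8 / 1.8 = 31 fractions, which agrees with section 5.1. The 55.8 Gy figure is correct for the standard boost.

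**Coverage dose in 12.31.** 0.95 x 55.8 = 53.01 Gy.

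**Capped supratentorial boost.**

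- Total prescribed: 23.4 + 27 = 50.4 Gy (28 fractions).
- Coverage dose relative to prescription: 53.01 / 50.4 = 105.2%.
- Boost implied by 12.31: 53.01 - 23.4 = 29.61 Gy, against a cap of 27 Gy. The excess is 2.61 Gy (29.61 / 27 = 1.097, or 9.7%).
- Upper homogeneity limit in the central plane: 1.05 x 50.4 = 52.92 Gy, which is 0.09 Gy below 53.01 Gy.
- Floor: 50 / 50.4 = 99.2% of prescription. The relative rule in 12.44 would accept 0.95 x 50.4 = 47.88 Gy.

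**Spinal boosts, if 12.31 is general.**

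- 45 Gy deposits: 53.01 / 45 = 117.8% of prescription, and the floor is 50 / 45 = 111.1%.
- 50.4 Gy deposits: the same 105.2% and 99.2% as above.

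**Full-dose patients (55.8 Gy).** Away from the optic structures, a plan that meets 12.44 has at least 53.01 Gy over the whole PTV and so also meets 12.31. Where the PTV includes the chiasm or optic nerves, the limit is 50.4 / 55.8 = 90.3% of prescription, and 12.44 cannot be met there. The 95%-volume allowance and the 50 Gy floor in 12.31 and 12.34 can absorb a small overlap, within 50.4 - 50 = 0.4 Gy.

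| Prescribed total | 12.31 coverage | As % of prescription | 95% of own prescription |
|---|---|---|---|
| 55.8 Gy | 53.01 Gy | 95.0% | 53.01 Gy |
| 50.4 Gy | 53.01 Gy | 105.2% | 47.88 Gy |
| 45 Gy | 53.01 Gy | 117.8% | 42.75 Gy |

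**The case against.** The strongest reply is that 12.31 was never meant for these boosts. Its GTV, CTV and PTV text is almost the same as the posterior fossa text in 12.34. Its PTV (a 1.5 cm margin plus 0.3 to 0.5 cm) is not the 1 cm supratentorial volume of 12.32 and 12.35. When 12.532 sends supratentorial boosts to section 12.3, it goes on to the optic limit as something already noted there, and within 12.3 that limit appears only in 12.35. The 55.8 Gy in parentheses can be read as the standard case, with 12.44 supplying a relative rule for the rest. A competent planner would be unlikely to override an explicit large-volume cap because of a parenthesis.

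Most of this stands, and the limited reading is at least as natural as the literal one. It does not remove the contradiction. Section 12.31 carries no site limit, and no exemption is written. Outside 12.34, it is also the only place that defines the PTV on which 12.44 relies.

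Three stronger inferences are tempting, and the protocol does not support them:

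- A reader might infer that a capped patient's plan would fail the quality review. Section 12.7 describes a retrospective review with no pass or fail criterion and no reference to 12.31.
- A reader might infer that full-dose patients face no conflict and that the 95%-volume allowance and 50 Gy floor do no work. The optic overlap shown in the working refutes both.
- A reader might infer that only very large supratentorial boosts are touched. If 12.31 is general, it reaches the spinal boosts too.

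**Conclusion.** The contradiction is real but minor. Read literally, 12.31 demands 53.01 Gy where the protocol elsewhere prescribes 50.4 or 45 Gy. For a capped supratentorial boost this is 105.2% of prescription, 2.61 Gy above the boost cap and marginally above the +5% homogeneity limit, though within the 10% that 12.551 treats as the outer bound.

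This rests on reading 12.31 as general, as its form suggests. If it was meant only for 55.8 Gy posterior fossa boosts, which is probable, the conflict with lower prescriptions is one of drafting only. The separate tension between 12.44 and the optic limit remains on either reading.

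The protocol does not say how often boosts exceed 2/3 of the compartment. With about 10 patients planned, few can be affected and possibly none through the cap. No endpoint, sample size, error rate or stopping rule changes.

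**What to change.** In section 12.31, do one of the following:

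- Replace 55.8 Gy with the patient's own prescribed total dose, so that 95% means 53.01, 47.88 or 42.75 Gy for 55.8, 50.4 or 45 Gy. Restrict the 50 Gy floor to 55.8 Gy prescriptions as well, because it would otherwise remain above 47.88 Gy.
- State that both the 55.8 Gy figure and the 50 Gy floor apply only to 55.8 Gy prescriptions.

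In either case, add one sentence saying that the 27 Gy boost cap and the 50.4 Gy optic limit take precedence over the coverage rules in 12.31, 12.34 and 12.44. The study's radiation oncologist should confirm the intended wording.

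As a separate clerical correction, 12.523 refers 3D plans to section 12.45 for the prescription point, but section 12.4 ends at 12.44. Correct the reference, to 12.44 if that is what is meant.

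The cost is a protocol wording change, with no effect on design or analysis.

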### 12.32 Treatment Volume

The target volume for the initial portion of the treatment is the entire cranio-spinal axis (the entire subarachnoid space). The target volume for the boost is the tumor bed and the residual tumor if the primary site is in the infratentorial region of the brain. The target volume for the boost for supratentorial tumors is 1 cm around the tumor as seen on the pre-surgical MRI scan. Metastatic tumors will receive boost irradiation with a 1 cm margin around the tumor as seen on a pretreatment MRI scan. 3D treatment planning may be used to plan the boost portion of the treatment.

### 12.33 Cranio-Spinal Axis

The cranio-spinal axis comprises the whole brain as well as the spinal cord and thecal sac. The whole brain treatment volume should extend anteriorly to include the entire frontal lobe and cribriform plate region. The superior orbital tissue (but not the posterior globe) should be included in the volume. The treatment volume should extend at least 0.5 cm inferiorly below the base of the skull. The volume should extend inferiorly to the superior border of the spinal field. The spinal treatment volume should extend laterally to cover the recesses of the entire vertebral bodies, with at least a 1.0 cm margin on either side. It should extend superiorly to the border with the cranial field and inferiorly 1-2 cm below the termination of the thecal sac. This position should be determined from a sagittal MRI and will always be at least as low as the inferior border of the S2 and may extend to S4. A "spade" field may be required to obtain a 1.0 cm margin around the subarachnoid space at the level of the sacrum. The objective is to include the nerve roots as they exit the neural foramina.

